8.1.2 Laboratory test abnormalities

8.1.2.1 Definitions and reporting

Laboratory abnormalities that constitute an Adverse event in their own right (are considered clinically significant, induce clinical signs or symptoms, require concomitant therapy or require changes in study treatment), should be recorded on the Adverse Events CRF. Whenever possible, a diagnosis, rather than a symptom should be provided (e.g. anemia instead of low hemoglobin). Laboratory abnormalities that meet the criteria for Adverse Events should be followed until they have returned to normal or an adequate explanation of the abnormality is found. When an abnormal laboratory or test result corresponds to a sign/symptom of an already reported adverse event, it is not necessary to separately record the lab/test result as an additional event.

Laboratory abnormalities, that do not meet the definition of an adverse event, should not be reported as adverse events. A Grade 3 or 4 event (severe) as per CTCAE does not automatically indicate a SAE unless it meets the definition of serious as defined below and/or as per investigator's discretion. A dose hold or medication for the lab abnormality may be required by the protocol in which case the lab abnormality would still, by definition, be an adverse event and must be reported as such.

8.1.3 Adverse events of special interest

8.2 Serious adverse events

8.2.1 Definitions

Serious adverse event (SAE) is defined as one of the following:

- Is fatal or life-threatening
- Results in persistent or significant disability/incapacity
- Constitutes a congenital anomaly/birth defect
- Is medically significant, i.e., defined as an event that jeopardizes the patient or may require medical or surgical intervention to prevent one of the outcomes listed above
- Requires inpatient hospitalization or prolongation of existing hospitalization,

Note that hospitalizations for the following reasons should not be reported as serious adverse events:

- Routine treatment or monitoring of the studied indication, not associated with any deterioration in condition
- Elective or pre-planned treatment for a pre-existing condition that is unrelated to the indication under study and has not worsened since signing the informed consent
- Social reasons and respite care in the absence of any deterioration in the patient's general condition

Note that treatment on an emergency outpatient basis that does not result in hospital admission and involves an event not fulfilling any of the definitions of a SAE given above is not a serious adverse event.

8.2.2 Reporting

To ensure patient safety, every SAE, regardless of suspected causality, occurring after the patient has provided informed consent

and until at least 30 days after the patient has stopped study treatment must be reported to Novartis within 24 hours of learning of its occurrence.

Any additional information for the SAE including complications, progression of the initial SAE, and recurrent episodes must be reported as follow-up to the original episode within 24 hours of the investigator receiving the follow-up information. An SAE occurring at a different time interval or otherwise considered completely unrelated to a previously reported one should be reported separately as a new event.

Any SAEs experienced after the 30 day safety evaluation follow-up should only be reported to Novartis if the investigator suspects a causal relationship to the study treatment.

Information about all SAEs is collected and recorded on the Serious Adverse Event Report Form; all applicable sections of the form must be completed in order to provide a clinically thorough report. The investigator must assess and record the relationship of each SAE to each specific study treatment (if there is more than one study treatment), complete the SAE Report Form in English, and submit the completed form within 24 hours to Novartis. Detailed instructions regarding the SAE submission process and requirements for signatures are to be found in the investigator folder provided to each site

Follow-up information is submitted in the same way as the original SAE Report. Each re-occurrence, complication, or progression of the original event should be reported as a follow-up to that event regardless of when it occurs. The follow-up information should describe whether the event has resolved or continues, if and how it was treated, whether the blind was broken or not, and whether the patient continued or withdrew from study participation.

If the SAE is not previously documented in the Investigator's Brochure or Package Insert (new occurrence) and is thought to be related to the Novartis study treatment, an oncology Novartis Drug Safety and Epidemiology (DS&E) department associate may urgently require further information from the investigator for Health Authority reporting. Novartis may need to issue an Investigator Notification (IN), to inform all investigators involved in any study with the same drug that this SAE has been reported. Suspected Unexpected Serious Adverse

Reactions (SUSARs) will be collected and reported to the competent authorities and relevant ethics committees in accordance with Directive 2001/20/EC or as per national regulatory requirements in participating countries.

8.3 Pregnancies

To ensure patient safety, each pregnancy occurring while the patient is on study treatment must be reported to Novartis within 24 hours of learning of its occurrence. The pregnancy should be followed up to determine outcome, including spontaneous or voluntary termination, details of the birth, and the presence or absence of any birth defects, congenital abnormalities, or maternal and/or newborn complications.

Pregnancy should be recorded on a Clinical Trial Pregnancy Form and reported by the investigator to the oncology Novartis Drug Safety and Epidemiology Department (DS&E). Pregnancy follow-up should be recorded on the same form and should include an assessment of the possible relationship to the study treatment of any pregnancy outcome. Any SAE experienced during pregnancy must be reported on the SAE Report Form.

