Stage related to study timeline	A major subdivision of the study timeline; begins and ends with major study milestones such as enrollment, randomization, completion of treatment, etc.
Stop study participation	Point/time at which the patient came in for a final evaluation visit or when study treatment was discontinued whichever is later
Study treatment	Includes any drug or combination of drugs in any study arm administered to the patient (subject) as part of the required study procedures, including placebo and active drug run-ins. In specific examples, it is important to judge investigational treatment component relationship relative to a study treatment combination; study treatment in this case refers to the investigational and non-investigational treatments in combination.
Study treatment discontinuation	Point/time when patient permanently stops taking study treatment for any reason
Variable	Identifier used in the data analysis; derived directly or indirectly from data collected using specified assessments at specified timepoints
Withdrawal of consent	Withdrawal of consent occurs only when a patient does not want to participate in the study any longer, and does not want any further visits or assessments, and does not want any further study related contact

Protocol summary:

Title	A multicenter phase II, open label, single arm study to evaluate the efficacy and safety of ruxolitinib in the treatment of anemic myelofibrosis patients.
Brief title	Anemia trial in MF patients
Sponsor and Clinical Phase	Novartis Phase II
Investigation type	Drug
Study type	Interventional
Purpose and rationale	This is a study of treatment with ruxolitinib in patients who present with transfusion dependent or independent anemia at screening defined as an hemoglobin <10 g/dL with 10 mg BID starting dose with subsequent up titrations depending on safety and efficacy. This dosing approach for anemic MF patients will be systematically studied in this prospective multicenter phase II open label single arm trial to determine if the levels of spleen length reduction and symptom improvement are consistent with those reported in previous clinical trials with ruxolitinib in patients with anemia and doses according to platelet counts at the moment of treatment initiation, and whether this lower starting dose and up titration approach may minimize the initial hemoglobin and platelet declines and transfusion requirements.

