14. Significant concurrent, uncontrolled medical condition which, in the investigator's opinion, would jeopardize the safety of the patient or compliance with the protocol.
15. Patients undergoing treatment with another investigational medication or having been treated with an investigational medication within 30 days or 5 half-lives (whichever is longer) prior to the first dose of study drug.
16. Patients with a history of malignancy in the past 3 years, except for treated early stage squamous or basal cell carcinoma.
17. Patients who are unable to comprehend or are unwilling to sign an ICF.
18. Pregnant or nursing (lactating) women
19. Women of child-bearing potential, defined as all women physiologically capable of becoming pregnant, unless they are using highly effective methods of contraception throughout the study duration inclusive of 30 day safety follow up. Highly effective contraception methods include:
 - a. Total abstinence (when this is in line with the preferred and usual lifestyle of the patient). Periodic abstinence (e.g., calendar, ovulation, symptothermal, post-ovulation methods) and withdrawal are not acceptable methods of contraception
 - b. Female sterilization (have had surgical bilateral oophorectomy with or without hysterectomy), total hysterectomy or tubal ligation at least six weeks before taking study treatment. In case of oophorectomy alone, only when the reproductive status of the woman has been confirmed by follow up hormone level assessment
 - c. Male sterilization (at least 6 months prior to screening). The vasectomized male partner should be the sole partner for that patient.
 - d. Use of oral, injected or implanted hormonal methods of contraception or placement of an intrauterine device (IUD) or intrauterine system (IUS) or other forms of hormonal contraception that have comparable efficacy (failure rate <1%), for example hormone vaginal ring or transdermal hormone contraception (in case of oral contraception you should have been using the same pill on a stable dose for a minimum of 3 months before screening)

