Chemistry	Albumin, Alkaline phosphatase, ALT , AST , Gamma-glutamyl-transferase (GGT), Lactate dehydrogenase (LDH), Calcium, Magnesium, Phosphorus, Sodium, Potassium, Creatinine, Creatine kinase, Direct Bilirubin, Total Bilirubin, Total Cholesterol, LDL Cholesterol, HDL Cholesterol, Total Protein, Triglycerides (fasting), Blood Urea Nitrogen (BUN) or Urea, Uric Acid Amylase, Lipase, Glucose (fasting)
Viral Hepatitis	For hepatitis B: HB-sAG and anti HB-c antibody at screening. For Hepatitis C: anti HCV antibody at screening. For patients with inactive infection, testing every 12 weeks for reactivation (for HBV) and at regular intervals as per the local practice (for HCV).
Pregnancy Test	A serum pregnancy test should be performed at screening and EOT visit, while at all other timepoints, urinary pregnancy tests are sufficient.

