8.1 Adverse events

8.1.1 Definitions and reporting

An adverse event is defined as the appearance of (or worsening of any pre-existing) undesirable sign(s), symptom(s), or medical condition(s) that occur after patient's signed informed consent has been obtained.

Abnormal laboratory values or test results occurring after informed consent constitute adverse events only if they induce clinical signs or symptoms, are considered clinically significant, require therapy (e.g., hematologic abnormality that requires transfusion or hematological stem cell support), or require changes in study medication(s).

Adverse events that begin or worsen after informed consent should be recorded in the Adverse Events CRF. Conditions that were already present at the time of informed consent should be recorded in the Medical History page of the patient's CRF. Adverse event monitoring should be continued for at least 30 days following the last dose of study treatment. Adverse events (including lab abnormalities that constitute AEs) should be described using a diagnosis whenever possible, rather than individual underlying signs and symptoms. When a clear diagnosis cannot be identified, each sign or symptom should be reported as a separate Adverse Event.

Adverse events will be assessed and graded according to the Common Terminology Criteria for Adverse Events (CTCAE) version 4.03. Grade 1 to 5 will be used to characterize the severity of the Adverse Event.

If CTCAE grading does not exist for an adverse event, the severity of mild, moderate, severe, life-threatening, and death related to the AE corresponding respectively to Grades 1 - 5, will be used. Information about any deaths (related to an Adverse Event or not) will also be collected through a Death form.

The occurrence of adverse events should be sought by non-directive questioning of the patient during the screening process after signing informed consent and at each visit during the study. Adverse events also may be detected when they are volunteered by the patient during the screening process or between visits, or through physical examination, laboratory test, or other assessments. As far as possible, each adverse event should be evaluated to determine:

1. The severity grade (CTCAE Grade 1-5)
2. Its duration (Start and end dates)

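### Section 8.3 does not require reporting or outcome follow-up of a pregnancy conceived in the 30 days after the last dose, although contraception and SAE reporting run through that period

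*Protocol*

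**What the plan says.** Protocol Section 8.3 sets the pregnancy rule: "each pregnancy occurring while the patient is on study treatment must be reported to Novartis within 24 hours". The 24 hours run from learning of the pregnancy. The section then asks for follow-up to outcome, including birth details, abnormalities and possible relation to study treatment, and for any SAE during pregnancy to go on the SAE form. It names no period after treatment.

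The neighbouring rules do name one:

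- Section 5.3, exclusion 19, excludes women of child-bearing potential "unless they are using highly effective methods of contraception throughout the study duration inclusive of 30 day safety follow up".
- Section 8.1.1: "Adverse event monitoring should be continued for at least 30 days following the last dose of study treatment".
- Section 8.2.2 makes every SAE after consent reportable, whatever its suspected cause, "and until at least 30 days after the patient has stopped study treatment must be reported to Novartis within 24 hours". After that, only SAEs suspected to be related are reportable.

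On testing, Table 7-2 says "A serum pregnancy test should be performed at screening and EOT visit", with urine tests at the other time points. Table 7-1 marks no pregnancy test at the 30-day safety follow-up, and Section 7.1.6 lists none.

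**The concern.** The other post-dose safety provisions run for 30 days (at least 30 for adverse events and SAEs). The pregnancy rule, read as written, stops with treatment. A woman is asked to avoid conception for 30 days after her last dose, but if contraception fails in that time the site has no stated duty to report it.

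What is at stake is safety information, not efficacy. Section 8.3 is the only text that asks for a pregnancy as such to be followed to outcome. Section 1.2.1.2.3 and the appended label (Appendix 6, label section 4.6) say that the drug is embryotoxic and foetotoxic in animals, that there are no data in pregnant women, and that the human risk is unknown. With so little known, each possibly exposed pregnancy is worth recording.

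**Working it through.** No sample size, error rate or event count enters this point. The check sets the windows side by side and then traces the possible cases.

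**Days covered after the last dose**

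| Rule | Place in Protocol | Days |
|---|---|---|
| Contraception | 5.3, exclusion 19 | 30 |
| Safety evaluations | 4.1 and 7.1.6 | 30 |
| Adverse event monitoring | 8.1.1 | at least 30 |
| SAE reporting, any causality | 8.2.2 | at least 30 |
| Pregnancy reporting and outcome follow-up | 8.3 | none stated |

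Gap = 30 − 0 = 30 days for each woman of child-bearing potential.

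**When a patient stops being on study treatment.** Section 8.3 does not define the phrase. The Protocol glossary defines study treatment discontinuation as "Point/time when patient permanently stops taking study treatment for any reason". On that reading the Section 8.3 window closes at the permanent stop. No other rule in the Protocol or SAP requires a report of a pregnancy that begins later.

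**Cases**

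1. Conceived before the last dose, recognised at any later time: covered. The trigger is when the pregnancy occurred, and the clock starts when the site learns of it.
2. Conceived on days 1 to 30 after the last dose, uncomplicated: no required report and no required follow-up.
3. Conceived on days 1 to 30, with an SAE within the 30 days: the SAE is reportable under Section 8.2.2 regardless of causality.
4. Conceived on days 1 to 30, with an SAE after day 30: reportable only if the investigator suspects a causal relationship. Section 8.2.1 counts a congenital anomaly as an SAE, but an anomaly in a pregnancy this recent would normally be found well after day 30.

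The gap is therefore case 2, plus those outcomes in case 4 that are judged unrelated.

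**Likely exposure in the gap.** Section 1.2.1.2.1 gives a mean half-life of about 3 hours with no appreciable accumulation. Taking five half-lives as washout (my assumption), 5 × 3 = 15 hours. With the 6.0-hour half-life that the label reports alongside ketoconazole, 5 × 6.0 = 30 hours. Thirty days is 30 × 24 = 720 hours, so drug would be present for about 15/720 = 2% to 30/720 = 4% of the period.

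**Likely number of patients.** The target is 50 (Section 4.1), and median age at diagnosis is about 65 years (Section 1.1). The documents do not give the number of women of child-bearing potential. Adults from 18 years are eligible, and the schedule provides for pregnancy tests, so the number is not zero by design.

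**The case against.** The strongest case against has three parts.

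First, the windows serve different purposes and need not be equal. Contraception can run longer as a precaution, while pregnancy reporting is limited to exposed pregnancies. The half-life supports this, and the appended label asks for contraception only during treatment. This stands as a reason to rate the point low. It does not make the text complete: conception within hours of the last dose can still meet drug, conception near the last dose is hard to date, and the protocol gives no reason for setting 30 days for one duty and none for the other.

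Second, Protocol Section 10.5.3.1 and SAP Section 2.1.1 define an on-treatment period that ends 30 days after the last dose. Carried over to Section 8.3, that definition would close the gap. But it groups data for the safety analyses, Section 8.3 does not refer to it, and Section 8.2.2 spells out the 30 days where they are meant. It shows that the phrase can be read two ways, which is itself a reason to settle it.

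Third, SAE reporting is a backstop. This is true for cases 3 and 4 within the limits shown, but an uncomplicated pregnancy is not an SAE.

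A reader might also infer that the protocol regards foetal risk as lasting 30 days. The documents do not say so. They call the period safety follow-up.

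**Conclusion.** The point holds as a minor gap. As written, Section 8.3 does not require report or follow-up of a pregnancy conceived in the 30 days after the last dose unless an SAE reportable under Section 8.2.2 arises. This rests on reading on study treatment in its ordinary sense, as the glossary supports.

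Two stronger readings are tempting and should not be made:

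- That a pregnancy begun near the end of treatment and recognised only afterwards is missed. Section 8.3 covers it, because the rule turns on when the pregnancy occurred.
- That such cases are wholly lost to follow-up. The text removes a requirement but forbids nothing, and SAE reporting still catches some outcomes, including a birth defect that the investigator suspects is related.

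Very few patients are likely to be affected, and drug exposure in the gap is short. The primary endpoint, the success criteria and all other study results are unchanged.

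**What to change.** In Section 8.3, after the condition that the patient is on study treatment, add: *or within 30 days after the last dose*. This aligns the end of the pregnancy window with exclusion 19 and Section 8.2.2. The start of the window need not change.

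The cost is one phrase in the next amendment, and possibly a few extra pregnancy forms and follow-ups. No test or visit has to be added. As no pregnancy test is scheduled at the 30-day follow-up, detection in that period would depend on the patient reporting it.

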8.4 Warnings and precautions

No evidence available at the time of the approval of this study protocol indicated that special warnings or precautions were appropriate, other than those noted in the provided Investigator Brochure. Additional safety information collected between IB updates will be communicated in the form of Investigator Notifications. This information will be included in the patient informed consent and should be discussed with the patient during the study as needed.

8.5 Data Monitoring Committee

Not applicable

8.6 Steering Committee

The steering committee will be established comprising investigators participating in the trial, i.e. not being members of the DMC and Novartis representatives from the Clinical Trial Team.

[figure not shown]
The SC will ensure transparent management of the study according to the protocol through recommending and approving modifications as circumstances require. The SC will review protocol amendments as appropriate. Together with the clinical trial team, the SC will also develop recommendations for publications of study results including authorship rules. The details of the role of the Steering Committee will be defined in a Steering Committee charter.

9 Data collection and management

9.1 Data confidentiality

Information about study patients will be kept confidential and managed under the applicable laws and regulations. Those regulations require a signed patient authorization informing the patient of the following:

- What protected health information (PHI) will be collected from patients in this study

- Who will have access to that information and why
- Who will use or disclose that information
- The rights of a research subject/patient to revoke their authorization for use of their PHI.

In the event that a patient revokes authorization to collect or use PHI, the investigator, by regulation, retains the ability to use all information collected prior to the revocation of patient authorization. For patients that have revoked authorization to collect or use PHI, attempts should be made to obtain permission to collect follow-up safety information (e.g. has the patient experienced any new or worsened AEs) at the end of their scheduled study period.

The data collection system for this study uses built-in security features to encrypt all data for transmission in both directions, preventing unauthorized access to confidential participant information. Access to the system will be controlled by a sequence of individually assigned user identification codes and passwords, made available only to authorized personnel who have completed prerequisite training.

[figure not shown]
Prior to entering key sensitive personally identifiable information (Patient Initials and exact Date of Birth), the system will prompt site to verify that this data is allowed to be collected. If the site indicates that country rules or ethics committee standards do not permit collection of these items, the system will not solicit Patient Initials. Year of birth will be solicited (in the place of exact date of birth) to establish that the patient satisfies protocol age requirements and to enable appropriate age-related normal ranges to be used in assessing laboratory test results.

